7.3 Study procedures

The study coordinator checks the diagnose lists of the department of Traumatology and Orthopedics, and identifies the female DRF-patients in the age of 45-75 years of age, who are conservatively treated. These patients will be randomly allocated to the experimental or control group. They receive an information letter and are asked to participate. When they decide to participate, they return an informed consent. When the patients visit the hospital for a medical check one week after initial treatment, the patients who are willing to participate are asked to fill out the Vividness of Motor Imagery Questionnaire. A score of 72 point or less on the internal scale (first person perspective) of the VMIQ, is one of the inclusion criteria. Therefore, this questionnaire is filled out before inclusion. The score on the VMIQ determines whether the patient can participate in the study or not. The patients who are allocated to the experimental group will receive information and instructions about the motor imagery training. To promote the imagery, the instructions are task-related:

- Flexion and extension: Patients are asked to imagine making a fist and imagine that they are slowly knocking on the table with their knuckles, making an exaggerated large movement.
- Adduction and abduction: Patients are asked to imagine that there are two dots drawn horizontally on the table in front of them. The hand lies between those dots, but there is still space between the hand and the dots. They are asked to imagine that they are trying to touch the right and the left dot with their little finger and thumb repeatedly, by only moving the palm of their hand.
- Pronation and supination: Patients are asked to imagine that they turn a key back and forth, by only using their hand and forearm.

In addition to these task-related instructions, the movements that have to be imagined are demonstrated by the study coordinator. Next, the patients are asked to repeat that movement once with their uninjured hand. The patients receive a letter that contains the instructions and are asked to repeat this protocol unsupervised at home. To promote their adherence to the motor imagery training, the patients in the experimental group will be contacted by phone on a weekly basis. To control for bias as a consequence of this extra attention, also the patients in the control group will be contacted by phone weekly.

Three weeks later, which is 4 weeks after injury, the patients return to the hospital to remove the cast. At that moment, the first measurements will be performed. All tests will be performed by the study coordinator. Directly after cast removal, when they are still at the hospital, dexterity, the level of pain and pain relief, grip strength and range of motion will be determined. The PRWHE will be performed one day later by phone. Two weeks after cast removal, the second measurements will be conducted. Function, dexterity, the level of pain and pain relief, grip strength and range of motion will be measured.

The measurements will take place in the University Medical Center Groningen. The PRWHE and the VAS can be scored by the patients themselves, while the measurements with the SODA, goniometer and dynamometer will be conducted by the study coordinator. It is expected that the first measurements will take 30 minutes to complete, and the second measurements 35 minutes.

As explained in chapter 7.1, function is measured using the PRWHE. The PRWHE is a self-reporting instrument that determines the level of disability during specific and usual activities, and also contains some items to determine the level of pain and aesthetics (59). It takes on average 4 minutes to complete the questionnaire (61).

A digital goniometer is used to determine the active ROM. It is expected that the process of measuring ROM takes 6 minutes to complete.

Grip strength is measured using a hydraulic dynamometer (73). The strength of four different grips will be determined, according to the protocol as described by Mathiowetz et al. (1984). It is expected that the procedure to measure the grip strengths takes 4 minutes to measure both sides.

Dexterity is determined using the SODA. The SODA is a performance-based test, which measures the level of disability during activities of daily living (68). We expect that it takes 20 minutes to complete it. Instructions of the SODA will be given according to the protocol described by Van Lankveld et al. (1996).

The level of pain and the level of pain relief are determined using a VAS (75), a self-reporting scale. It is expected that it only will take a few seconds to complete it.

7.4 *Withdrawal of individual subjects*

The patients are free to withdraw from the study at any time, for any reason, and without consequences. Patients are withdrawn when the study coordinator thinks that participation by a

patient is unsafe, or when the medical condition changes in such way that participation is impossible or unadvised.

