3. STUDY DESIGN

The above hypothesis can be tested by conducting a parallel-group randomized controlled trial. The duration of this study is 5 weeks, depending on the length of the immobilization period. The patients will be measured during their visits to the hospital. The first measurement is conducted directly after removal of the cast. The second measurement is two weeks later, when the patients visit the hospital for their check-up appointment. A schematic view of the study is given below:

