6.7 Preparation and labeling of Investigational Medicinal Product

6.8 Drug accountability

7. METHODS

7.1 *Study parameters*

Based on literature about the outcome following a DRF (19-24), and experts' opinions, we decided to use 5 outcome measures. The main outcome measure is function. Other outcome measures used are the range of motion, grip strength, dexterity, and pain.

7.1.1 *Main study parameter/endpoint*

Research has shown that DRF-patients suffer more on long term from function restrictions than pain (15,16). Therefore, function is the main outcome measure. Function is measured using the Patient Rated Wrist/Hand Evaluation (PRWHE). This instrument is developed to measure disability during usual and specific activities, and it also documents pain and aesthetics. The PRWHE is derived from the PRWE and contains some extra questions about aesthetics. Because the PRWHE retains the originally validated questions, format and scoring system of the PRWE, it can be treated as the PRWE (59). A study that critically reviewed the available outcome assessment tools, showed that the PRWE is the most responsive instrument to measure outcome in DRF-patients (60). The PRWE is a self-rated questionnaire, and its mean completion time is 4 minutes (61). It consists of 15 questions, divided in 3 domains; pain, functional activities, and usual activities. The patients have to rate the severity of their pain or disability in different situations. The final score of the PRWE and PRWHE lies between 0-100, where 0 represents the best and 100 represents the worst outcome. The PRWE is found to be reliable and valid, and therefore provides a simple and quick method to measure patient-rated pain and disability (61).

7.1.2 *Secondary study parameters/endpoints*

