7.2 Randomization, blinding and treatment allocation

Potential participants are randomly allocated to the experimental or control group before the start of the study, i.e. before inclusion. In this way, the potential participants allocated to the control group can receive other information about this study than potential participants allocated to the experimental group. This is done to prevent occurrence of the bias that might be present when the patients in the control group are aware of the working mechanism of motor imagery, and its potential benefits. When the patients in the control group know that they participate in a study that is conducted to determine whether motor imagery can promote the recovery after DRF, it is possible that they perform motor imagery during the immobilization, or pay more attention to their injured hand as normal. Such bias cannot be detected and may severely confound the results of this study. Therefore, we decided to keep the patients in the control group ignorant.

Because randomization is performed before inclusion, it is likely that some patients will decide not to participate, reducing the number of participants in that group. The experience of 2.5 years inclusion teaches us that the response rate to participate is different for each group (experimental group 35%, control group 62%). Therefore, the number of patients who will be asked to participate is controlled for this difference. This means that more patients are allocated to the experimental group, than to the control group. The random allocation is performed with remaining equal group sizes, and equal distribution of the different fracture types (intra-articular vs. extra-articular distal radius fractures).

The randomization process is done using PASW Statistics 18. Subject numbers are randomly allocated to the experimental or the control group. The order in which the patients receive their initial treatment determines their subject number. There is no blinding of the patients, nor the researcher is blinded.

Based on national statistics concerning the diseases and injuries diagnosed on a yearly basis, it is expected that 6-7 DRF-patients will be treated in the UMCG every week, and 2-3 of them will be women of 45-75 years of age (58).

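### The primary PRWHE is taken by phone at T1, apparently by the unblinded coordinator, and its mode at T2 is not fixed, so arm-specific interviewer influence could enter the T1 comparison

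*Combined protocol and SAP*

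**What the plan says.** Section 7.3 places the T1 measurements at cast removal, except for the primary outcome: "The PRWHE will be performed one day later by phone". The sentence names no caller. Shortly before it, the section states: "All tests will be performed by the study coordinator". Section 7.2 states: "There is no blinding of the patients, nor the researcher is blinded". The coordinator necessarily knows the allocation of the experimental patients, because in section 7.3 "the movements that have to be imagined are demonstrated by the study coordinator".

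For T2, section 3 says: "The second measurement is two weeks later, when the patients visit the hospital for their check-up appointment". Section 7.3 adds: "Function, dexterity, the level of pain and pain relief, grip strength and range of motion will be measured". No phone call is mentioned for T2. A later sentence in 7.3 says "The PRWHE and the VAS can be scored by the patients themselves", while the SODA, goniometer and dynamometer are left to the coordinator. That sentence is not limited to either time point.

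Section 7.1.1 describes the parent instrument: "The PRWE is a self-rated questionnaire". The protocol gives no interview script, no independent or blinded caller and no common mode. The analysis in section 9.3 uses group and time as factors and does not mention mode.

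**The concern.** A self-rated questionnaire appears to be administered by voice at one of two time points, by someone who knows the arm and taught the intervention to one arm only. Two effects need to be kept apart.

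- **Mode effect common to both arms** (phone against paper). It shifts both arms equally at T1. It distorts the estimated recovery from T1 to T2 but cancels from every between-group comparison.
- **Arm-specific interviewer influence** (how the caller reads or records answers, or how freely a patient answers the person who showed her the exercise). It does not cancel. It goes straight into the T1 group contrast, and its excess over any similar influence at T2 goes into the group-by-time interaction.

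Both comparisons matter here. Section 9.3 compares the groups at each measurement time, and section 4.4 sizes the trial on the within-between interaction.

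**Working it through.** **Mode and administrator, side by side**

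| | T1 | T2 |
|---|---|---|
| Setting of PRWHE | Phone, one day after cast removal (7.3) | Hospital check-up (3, 7.3) |
| Administrator | Not named; coordinator by inference from the all-tests sentence (7.3) | Self-completion permitted, not required (7.3) |
| Visit length stated | 30 min | 35 min |

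The timings in 7.1.2 and 7.3 fit this reading. SODA 20 + range of motion 6 + grip 4 = 30 minutes, the stated T1 length. Adding the 4-minute PRWHE gives 34, close to the 35 stated for T2. So the PRWHE falls inside the T2 visit only. The timings do not show how it is completed there.

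**The plan's own figure.** Section 4.4 inputs: effect size 0.20, α = 5%, power 80%, two groups, two measurements, other settings at default (correlation ρ = 0.5 and sphericity assumed as those defaults). With 0.20 read as Cohen's f:

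- λ = f² × N × m / (1 − ρ) = 0.04 × 52 × 2 / 0.5 = 8.32, with df 1 and 50
- Power = 0.807 at N = 52 and 0.791 at N = 50, so the stated 52 is reproduced.

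Whether 0.20 belongs in that field is a separate question and does not affect this point.

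**Illustration of a T1 differential of b points.** Inputs: 26 per group (52 in equal groups), SD 26.13 (4.4), ρ assumed at 0.5 with range 0.3 to 0.7. The documents give no value for b.

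- SE of the group-by-time contrast = SD × √(2(1 − ρ)) × √(2/26)
- At ρ = 0.5: 26.13 × 1 × 0.277 = 7.2 points. At ρ = 0.3: 8.6. At ρ = 0.7: 5.6.
- Two-sided rejection rate with no true effect = 1 − Φ(1.96 − b/SE) + Φ(−1.96 − b/SE)

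| b (points) | ρ = 0.3 | ρ = 0.5 | ρ = 0.7 |
|---|---|---|---|
| 0 | 5.0% | 5.0% | 5.0% |
| 2 | 5.6% | 5.9% | 6.5% |
| 3 | 6.4% | 7.0% | 8.3% |
| 5 | 9.0% | 10.6% | 14.5% |

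The T1 group contrast has SE = 26.13 × √(2/26) = 7.2 whatever ρ is, so the ρ = 0.5 column applies to it as well.

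**Direction.** Lower PRWHE scores are better. A T1 shift favouring training lowers the experimental T1 mean by b. The T1 contrast then looks better by b, and the experimental arm's T1-T2 decrease is smaller by b. Section 4.4 expects an extra decrease of 5 points. With b = 2 or 3, present at T1 only, the expected observed value is 5 − 2 = 3 or 5 − 3 = 2 points. The same bias can therefore flatter one planned comparison and mask the other.

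**The case against.** The best reply is that much of this rests on inference and that the effect is small.

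- **The caller is inferred.** The sentence on the T1 call is passive. The sentence permitting self-scoring separates the PRWHE from the tests that the coordinator conducts. A reader might also infer that the coordinator makes the weekly calls, but 7.3 names no caller for those either. This stands, and the point is worded accordingly. The gap is itself a reason to specify the caller and the mode.
- **The T2 mode is inferred.** A reader might conclude that T2 is self-completed. The text only permits it, and not specifically at T2. This stands: the T2 mode is open and could vary between patients.
- **Unblinded patients can shade a written form too.** True. An arm difference that is equal at both times cancels from the interaction but stays in each group contrast. Self-completion removes the interviewer component, not reporting bias.
- **The plan already balances attention**, since 7.3 gives both arms weekly calls. This evens out contact but does not remove the coordinator's knowledge of the allocation.
- **The size is assumed and modest.** Three points is 3/26.13 = 0.11 SD. Setting a small shift against the 5-point target makes it look large, but nothing in the documents says that such a shift occurs.
- **Posted forms could be late.** Section 4.4 gives 5.3 points of recovery in the first week, or 5.3/7 = 0.76 points a day. A delay of 2.6 to 4.0 days in one arm only would recreate a 2 to 3 point difference. This is a fair warning. It is why the next-day call should stay as a prompt and the form should carry its completion date.

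**Conclusion.** The concern holds as a weakness in procedure, not as a demonstrated bias. A self-rated primary outcome is taken by phone at T1, apparently by the unblinded coordinator who also demonstrates the imagery, and the mode at T2 is not fixed. An arm-specific influence at T1 would bias the T1 contrast in full and the interaction by its excess over T2.

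The size is unknown. With 26 per group, SD 26.13 and an assumed correlation of 0.5, a 2 to 3 point differential takes the interaction's false-positive rate to 5.9-7.0%. Over correlations of 0.3 to 0.7 the range is 5.6-8.3%. A shift favouring training would work against the extra T1-T2 decrease on which the trial is sized.

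Two stronger readings are not supported. One is that the bias spoils the primary outcome as a whole: the T2 group contrast is unaffected by anything confined to the T1 call. The other is that T1 is where the effect should be largest: section 10.4 expects a better outcome at cast removal but does not rank the time points, and section 4.4 states its target for two weeks later.

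**What to change.** Amend section 7.3 as follows.

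1. Hand every patient the PRWHE form at cast removal, to complete herself the next day. Use the planned next-day call only as a prompt, with no answers taken. The dated form is posted or brought to the T2 visit.
2. At T2 use the same self-completed form, filled in before the coordinator's tests.
3. Record mode and completion date for every PRWHE. Start the new procedure on one date for both arms, so that mode is not tied to arm.
4. For patients already measured by phone, report a sensitivity analysis by mode.
5. Bring the summary and section 10.4, which place the first measurement directly after cast removal, into line with the next-day PRWHE.

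The cost is forms and postage and an amendment notified to the ethics committee (section 11.2). No visit or staff member is added. The downsides are a few late or missing forms, limited by the prompt and by collection at T2, and mixed T1 modes across the trial, since section 7.2 already refers to 2.5 years of inclusion. With 52 patients the analysis by mode will be imprecise. Reporting bias from unblinded patients remains and should be stated as a limitation.

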7.4.1 Specific criteria for withdrawal (if applicable)

Not applicable.

7.5 Replacement of individual subjects after redrawal

Individuals will be replaced after redrawal. The first eligible patient that presents at the first aid department will be allocated to the group of the redrawn patient, to remain equal group sizes.

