Sponsor	The sponsor is the party that commissions the organisation or performance of the research, for example a pharmaceutical company, academic hospital, scientific organisation or investigator. A party that provides funding for a study but does not commission it is not regarded as the sponsor, but referred to as a subsidising party.
SUSAR	Suspected Unexpected Serious Adverse Reaction
Wbp	Personal Data Protection Act (in Dutch: Wet Bescherming Persoonsgegevens)
WMO	Medical Research Involving Human Subjects Act (in Dutch: Wet Medisch-wetenschappelijk Onderzoek met Mensen)

SUMMARY

Rationale: Distal radius fracture (DRF) is a common injury that may lead to prolonged function restrictions, decreased range of motion, reduced grip strength and pain. These symptoms may be caused by physical changes due to the injury and/or by the 4-6 weeks immobilization that is part of the conservative treatment. However, it might also be that neural changes during the immobilization play an important role. Such changes might be prevented by motor imagery training during the immobilization period. So, when neural changes are prevented, this may lead to a better functional outcome.

Objective: The objective is to improve the functional outcome in distal radius fracture patients, specified as an increase in function, dexterity, grip strength, range of motion, and decrease of pain.

Study design: Parallel group randomized controlled trial, with a post-test only control group design. Patients in the experimental group perform motor imagery training during the immobilization period, in addition to the regular treatment. Patients in the control group receive regular treatment.

Study population: Female DRF-patients who are conservatively treated by a cast, aged 45-75 years. The fracture must be a low energy trauma caused by a fall. Patients with a score higher than 72 on the internal scale of the Vividness of Motor Imagery Questionnaire (VMIQ) are excluded, as well as patients with co-morbidities that might influence the wrist function, or motor imagery-ability, and patients with no understanding of Dutch language.

The patients are randomly allocated to the experimental or control group by restricted randomization to ensure equal group sizes. The randomization is conducted with use of PASW Statistics 18.

Intervention: Motor imagery training; 4 times a day 7 minutes of motor imagery training for 3 weeks (depending on duration of immobilization period).

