4.3 Exclusion criteria

- Internal Visual Motor Imagery Questionnaire-score ≥ 72
- Intra-articular, communitive fractures of the distal radius
- Complications likely resulting in worse functional outcome (e.g. dislocation)
- High energy trauma (such as car accidents or by falls from height)
- Pre-existent upper-extremity disorders
- No understanding of Dutch language

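### Sections 5.2 and 7.5 work against the intention-to-treat analysis of 9.3: patients reporting other treatment are dropped after their outcomes are measured, and replacement patients get their arm outside the random list

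*Combined protocol and SAP*

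**What the plan says.** All references are to the combined protocol and SAP.

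- **Random list.** Section 7.2: "Subject numbers are randomly allocated to the experimental or the control group". The order of initial treatment sets the subject number. The section also says: "The random allocation is performed with remaining equal group sizes, and equal distribution of the different fracture types". The summary describes allocation "by restricted randomization to ensure equal group sizes".
- **Blinding.** Section 7.2: "There is no blinding of the patients, nor the researcher is blinded".
- **Replacement.** Section 7.5 replaces withdrawn patients: "The first eligible patient that presents at the first aid department will be allocated to the group of the redrawn patient". The stated purpose is equal group sizes.
- **Follow-up after stopping treatment.** Section 7.6 follows these patients and regards their data as still informative. It does not mention their place in the analysis.
- **Other treatment.** Section 5.2 asks every patient, after the last measurements, about other interventions or treatments during the study, and omits the results of those who had any.
- **Analysis population.** Section 9.3 states that both groups are analysed by intention to treat.

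**The concern.** An intention-to-treat analysis keeps each participant in the arm to which chance assigned them, whatever happens later. Two rules depart from this.

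First, the 5.2 exclusion depends on something that happens after allocation, and it is ascertained once the outcomes exist, when patient and researcher both know the arm. It can therefore differ between arms.

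Second, under 7.5 a withdrawal decides the next patient's arm. That arm is known before the patient presents, and the rule takes no account of the fracture-type balance in 7.2. If replacements then stand in for the patients who withdrew, and patients with other treatment are removed, the result is nearer to a per-protocol comparison than to the one 9.3 promises. Because the plan does not settle this, more than one primary data set is compatible with its text.

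**Working it through.** **1. The passages side by side**

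| Patient | 9.3 implies | Other sections |
|---|---|---|
| Reports other treatment | analysed in allocated arm | 5.2: results omitted |
| Stops treatment, is followed up | analysed in allocated arm | 7.6: followed, analysis not stated; 7.5: replaced after withdrawal |
| Enters as a replacement | arm set by chance | 7.5: arm copied from the withdrawn patient |

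The first row is a contradiction. The second is a gap: it is also unclear whether stopping the training alone triggers 7.5, and only the experimental arm has an added training to stop. The third is a departure from 7.2.

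**2. The plan's sample size**

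Inputs from section 4.4: effect size 0.20, α = 5%, power 80%, 2 groups, 2 measurements, within-between interaction, other settings default. I assume the defaults are correlation 0.5 and no sphericity correction.

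λ = f²·N·m/(1 − ρ) = 0.04 × 52 × 2/0.5 = 8.32, on 1 and 50 degrees of freedom, gives power 0.807. N = 50 gives 0.791, so 52 is reproduced.

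This needs 0.20 to be entered as Cohen's f. Section 4.4 derives it as a mean difference over a standard deviation, which for two groups corresponds to f = 0.10 and power 0.29 at N = 52. That is a separate matter. I use the nominal 80% below only as a starting point and do not endorse it.

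**3. What equal group sizes are worth**

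Standard error ratio against 26/26: r = √[(1/a + 1/b)/(2/26)]. Power from a nominal 80%: Φ[(1.960 + 0.842)/r − 1.960].

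| Split | r | Power |
|---|---|---|
| 28/24 | 1.003 | 79.8% |
| 30/22 | 1.012 | 79.1% |
| 32/20 | 1.028 | 77.8% |
| 33/19 | 1.038 | 77.0% |

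The ratios r do not depend on the effect size.

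**4. Whether 7.5 restores balance**

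Section 7.2 gives response rates of 35% (experimental) and 62% (control). The arm-specific letter goes out within 48 hours (10.2) and the VMIQ follows at one week (7.3), so neither consent nor the VMIQ result is known when 7.5 sets the arm.

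- If 7.5 means one assignment per withdrawal, it yields a participant with probability at most 35% or 62%.
- If it means continuing until someone enters, each withdrawal takes on average at least 1/0.35 = 2.9 or 1/0.62 = 1.6 patients off the random list.

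The text does not say which is meant.

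**5. The allocation ratio matters more**

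At 1:1 allocation the expected split of 52 participants is 52 × 0.35/0.97 = 18.8 against 52 × 0.62/0.97 = 33.2. Section 7.2 corrects for this by allocating more patients to the experimental arm (0.62/0.35 = 1.77 to 1). An extended list must keep that ratio.

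**6. The 5.2 exclusion**

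One patient is 1/26 = 3.8% of an arm. The plan gives no rate. At an assumed 5% to 15% of 52, exclusion raises the standard error by √(52/49.4) = 1.026 to √(52/44.2) = 1.085. Keeping these patients therefore costs no sample size.

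**The case against.** **Few patients may be affected.** Section 5.2 expects no physiotherapy during the study. A reader might infer that the exclusion removes the patients who recover worst, because 5.2 mentions physiotherapy for severely affected hand function. The text does not support this: it places that advice more than two weeks after immobilization, and the last measurement is at two weeks. Complications might be another route, but 4.3 already excludes "Complications likely resulting in worse functional outcome". What remains is a contradiction with 9.3 whose consequences cannot be sized.

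**Taking the first eligible patient limits selection.** This stands. Nothing in the documents suggests that anyone steers patients. The objection to 7.5 is that it sets arms non-randomly for little gain. Equally, 7.2 describes no concealment of the list, so returning to the list restores chance assignment but does not by itself remove foreknowledge.

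**Unequal acceptance.** A reader might take 35% against 62% as a further defect. Section 7.2 discloses it and gives the reason for allocating before consent: informed controls might practise imagery or "pay more attention to their injured hand as normal". It is a reasoned design choice, and belongs in the report as a limit on the conclusion.

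**Covariates.** A reader might infer from the two factors named in 9.3 that there is no adjustment. Section 7.1.3 already commits to covariates, and a list of factors does not contradict that.

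**Conclusion.** The point holds in a bounded form. Sections 5.2 and 9.3 cannot both be followed. Section 7.5 sets some arms outside the random list, in an unblinded trial and without regard to fracture type. The plan also does not say that withdrawn patients are analysed alongside their replacements. This should be fixed before analysis.

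The conclusion rests on the text and not on any effect size. No withdrawal or co-intervention rate is given, so the size and direction of bias are unknown, and a claim that the result is biased towards either arm would go too far. What can be sized is the benefit of 7.5: it avoids a standard error increase of 0.3% to 3.8% for splits from 28/24 to 33/19. The second of these is about what 1:1 allocation would be expected to give, so smaller imbalances are likely as long as the ratio correction in 7.2 is kept.

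Separate and minor: a VMIQ score of exactly 72 excludes a patient under 4.1 and 4.3 but not under the summary, 7.3 and 10.2. These passages must be reconciled.

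**What to change.** 1. **Section 7.5.** Delete the assignment rule. Each new patient takes the next number on the random list, extended as needed with the same fracture-type balance and the same ratio correcting for 35%/62% acceptance. In the summary and 7.2, change equal group sizes to approximately equal. Section 7.2 refers to 2.5 years of inclusion, so some patients may already have been assigned under 7.5: report how many, and give a sensitivity analysis without them.
2. **Section 9.3.** Analyse all included participants by allocated arm, including those who stop treatment and are followed under 7.6 and those who report other treatment. State that a later recruit does not take a withdrawn patient's place in the analysis. Move the 5.2 exclusion to a sensitivity analysis.
3. **Reporting.** Give by arm the numbers allocated, declining, failing the VMIQ, withdrawn and meeting the 5.2 criterion. State the unequal acceptance as a limit on the conclusion.
4. **VMIQ.** Reconcile the passages to one rule.

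The cost is an amendment notified to the METC (11.2), a flow count and two sensitivity analyses, with no extra visits. There are two downsides. Groups will be slightly unequal, with the standard errors shown above. The primary estimate will include any effect of other treatments, and the sensitivity analysis will show the result without those patients.
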